- i. Presence of excessive pigment, bruises, scars, or tattoos around the potential injection area.
- j. Presence of any local skin infection, rash, or anything else that limits injection administration and assessment of injection site.
- k. Donated or received any blood or blood products (eg, white blood cells, platelets) within 60 days prior to screening, or has donated blood or blood products on 2 or more occasions within 6 months prior to IMP administration, or has donated plasma within 7 days prior to screening, or has planned donations during the 56 days or 5 half-lives following the last dose administration, whichever is longer. The minimum reference volume of whole blood lost or donated is 500 mL.
- l. Vulnerable participants (eg, prisoners or institutionalized individuals), participants who pose a significant risk of suicide attempt in the Investigator's judgment based on

medical history, answered “yes” to Suicidal Ideation items 4 or 5 on the [REDACTED] for “current” or “within 3 months prior to screening,” or had a suicide attempt or hospitalization due to suicide risk within 12 months prior to screening.

- m. 12-lead electrocardiogram (ECG) demonstrating intraventricular conduction delays (QRS interval \geq 110 msec or PR interval \geq 200 msec) and have a mean of triplicate QTcF values $>$ 450 msec for males and $>$ 470 msec for females at screening or other clinically significant ECG findings that would interfere with trial participation as judged by the Investigator.
- n. Personal or family history of arrhythmia, sudden unexplained death at a young age (before 40 years) in a first-degree relative, long QT syndrome, personal history of syncope, or history of uncontrolled high blood pressure. Participants with history of high blood pressure who no longer require treatment or participants who are treated with antihypertensive medications and whose blood pressure is currently well-controlled, may be enrolled.
- o. Supine or semi-supine blood pressure outside the range of 90 to 140 mm Hg for systolic or 50 to 90 mm Hg for diastolic (following at least a 5-minute rest). Note: If either value is out of range, blood pressure measurements may be repeated in the supine or semi-supine position at intervals of 5 to 10 minutes up to 2 times. If the systolic or diastolic measurement continues to exceed the stated limits, the participant will be excluded.

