- v. Use of an investigational drug or marketed drug (new chemical entity) within 30 days or 5 half-lives (whichever is longer) or in case of biologics (eg, tumor necrosis factor-alpha inhibitors such as adalimumab, etanercept, or infliximab) within 3 months or 5 half-lives (whichever is longer) prior to the administration of ZYPREXA im.
- w. Using or consuming the following concurrent medications, over-the-counter (OTC) products, prescription drugs (any route of administration: eg, oral, topical), or foods:
 - strong and moderate inducers or inhibitors of CYP1A2 (Section 13.4) within 30 days or 5 half-lives (whichever is longer) prior to the administration of ZYPREXA im.
 - dopamine reuptake inhibitors or prescription psychostimulants within 30 days prior to screening.
 - opioids or opioid-containing analgesics within 30 days prior to screening.
 - medications, in addition to those listed above, that may be expected to significantly interfere with the metabolism or excretion of olanzapine, that may be associated with a significant drug interaction with olanzapine, or that may pose a significant risk to participants if they were enrolled in the trial.
- x. Meets criteria for moderate to severe substance use disorder (based on DSM-5 criteria) within the past 6 months, such as chronic alcohol abuse or drug abuse (excluding those related to caffeine or nicotine). If, per the Investigator's judgment, a participant does not meet the criteria for substance use disorder, a positive result on the serum drug test is not exclusionary. Participant's eligibility in cases of a positive

result, without medical explanation, will be determined by the Investigator based on the participant's background, history of substance use, and the Investigator's discussions with family members, caregivers, or healthcare professionals, as applicable ([American Psychiatric Association 2013b](#)).

- y. Treatment-resistant schizophrenia according to medical and psychiatric history as judged by the Investigator or have taken clozapine for treatment-resistant schizophrenia.
- z. A significant sedation or delirium post-antipsychotic treatment according to medical and psychiatric history and as judged by the Investigator or suffered from delirium due to a medical condition.
 - aa. A significant risk of violent behavior based on the participant's medical and psychiatric history as judged by the Investigator.

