5.5. Ongoing Confirmation of Participant Eligibility

Participants' continued eligibility will be reconfirmed by review of abbreviated inclusion and exclusion criteria prior to administration of ZYPREXA im. The abbreviated list will include the following inclusion criteria (g, h) and exclusion criterion (a). Clinical scales and laboratory tests taken on day 1 will be used to confirm eligibility on day 3. In case of a delay, laboratory results can be reviewed to perform abbreviated eligibility assessment on day 4, as long as this is done prior to administration of ZYPREXA im. Laboratory results from blood samples collected on day 4 are not required prior to initiating ZYPREXA im. Day 4 central clinical laboratory

assessments will serve as baseline values and are based on samples collected prior to dosing of ZYPREXA im. Serology to support eligibility criteria will only be done at screening.

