6.8.1. Prohibited Concomitant Therapy

Participants will be excluded from participating in this trial if they are using or consuming the following concurrent medications, OTC products, prescription drugs (any route of administration: eg, oral, topical), or foods during the treatment periods (excluding follow-up):

- olanzapine products other than the IMPs of this trial.
- any antipsychotic medications other than the trial drug (excluding allowed antipsychotics during period 2 and follow-up period after period 3, and rescue medications that may be required to ensure the safety of participants during the trial, as described in Section 6.8.2).
- any of the following concurrent medications, OTC products, prescription drugs, or foods:

- strong or moderate inducers or inhibitors of CYP1A2 (Section 13.4) within 30 days or five half-lives (whichever is longer) prior to the administration of ZYPREXA im, whichever is longer
- dopamine reuptake inhibitors or prescription psychostimulants within 30 days prior to screening
- opioids or opioid-containing analgesics within 30 days prior to screening
- medications, in addition to those listed above, that may be expected to significantly interfere with the metabolism or excretion of olanzapine, that may be associated with a significant drug interaction with olanzapine, or that may pose a significant risk to participants in the trial

During the treatment periods, participants may not receive treatment with any other formulations or doses of olanzapine. Antipsychotics other than aripiprazole, risperidone, paliperidone, quetiapine, or lurasidone are not allowed during the screening period.

Any medications that interfere with the absorption, excretion, or metabolism of olanzapine, either directly or by liver enzyme induction or inhibition, are prohibited. A partial list of prohibited drugs can be found in Section 13.4.

In addition, during the follow-up periods, any restrictions on concomitant medications use that are included in the US labels of any of the antipsychotics allowed to be received per protocol (ie, aripiprazole, risperidone, paliperidone, quetiapine, or lurasidone) should be applied.

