8.3.2. Vital Signs

Vital signs, including body temperature, respiratory rate, supine or semi-supine pulse rate and blood pressure (systolic and diastolic), and their orthostatic changes, will be measured at the time points detailed in Table 1 to Table 5.

Orthostatic blood pressure and heart rate will be determined with measurements obtained after the participant has been supine or semi-supine for at least five minutes and repeated after the participant has been standing for 3 minutes.

All vital sign results outside of the reference range will be interpreted by the Investigator as belonging to 1 of the following categories:

- abnormal but not clinically significant
- abnormal and clinically significant

When applicable, vital signs will be measured after ECGs but before scheduled blood draws.

Before pulse, blood pressure, and respiratory rate are measured, the participants must be in a supine or semi-supine position and resting for at least 5 minutes. The same position and arm (opposite arm from the cannula site) should be used each time vital signs are measured for a given participant, when possible. For any abnormal vital signs finding, the measurement should be repeated as soon as possible.

Any vital sign result that is assessed by the Investigator as clinically significant will be recorded on the source documentation, transcribed to the CRF as an AE, and monitored as described in Section 8.4.4. In addition, potentially clinically significant values may be predefined by the Sponsor for selected vital signs and, if so, this will be documented in the Statistical Analysis Plan or other relevant documents (eg, medical monitoring plan).

8.3.3. *Electrocardiograms*

ECGs will be measured at the time points detailed in [Table 1](#) to [Table 5](#).

All ECG results outside of the reference range will be interpreted by a qualified physician as belonging to 1 of the following categories:

- abnormal but not clinically significant
- abnormal and clinically significant

When applicable, ECGs will be performed before vital signs measurements and scheduled blood draws. Before each ECG is performed, the participants must be in a supine or semi-supine position and resting for at least 5 minutes. At screening only, the ECG will be performed in triplicate at 5-minute intervals.

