7.10. Electrocardiography

ECGs will be measured at the time points detailed in Table 1 to Table 5 of the trial protocol.

Shifts (normal and abnormal) from baseline to each visit that it is measured will be summarized using patient counts. For overall finding, the summary will use the worst post-baseline finding for the patient (the abnormal finding if there are both normal and abnormal findings). Summary statistics for ECG variables will be presented at baseline and each visit. Actual values and changes from baseline to each visit will be summarized using descriptive statistics. The incidence of potentially clinically significant abnormal values for ECG variables will be summarized using descriptive statistics with the criteria specified below.

- QT interval corrected using Fridericia's formula (QTcF) values >450 msec, or >480 msec, or >500 msec.
- QTcF change from baseline values >30 , or >60 .
- PR change from baseline $\geq 25\%$ and value >200 .
- QRS change from baseline $\geq 25\%$ and value >110 .
- Heart rate value <60 bpm or >100 bpm.

[figure not shown]
The number (%) of participants with QTcF change from baseline values >30 , or >60 , will be also presented separately for Period 3 (day R1 to day R29)

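### Exclusion criterion m joins its QRS/PR limits to its QTcF limit with *and*, so read literally an isolated long QTcF, QRS or PR does not meet the numeric exclusion

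*Protocol*

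**What the plan says.** Any single exclusion criterion in Protocol Section 5.4 is enough to exclude, so each criterion has to work on its own wording. Criterion m has three parts:

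- a conduction part: QRS at or above 110 msec, or PR at or above 200 msec;
- a QTcF part, attached with "and have a mean of triplicate QTcF values" above 450 msec for men and 470 msec for women at screening;
- a judgment part, attached with *or*: any other ECG finding that the Investigator considers significant enough to interfere with participation.

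Neighbouring criteria let one abnormality suffice. Criterion n lists "in a first-degree relative, long QT syndrome" among histories that each exclude. Criterion o, on blood pressure, says "If the systolic or diastolic measurement continues to exceed the stated limits, the participant will be excluded".

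Protocol Section 8.3.3 adds that "All ECG results outside of the reference range will be interpreted by a qualified physician" and classed as clinically significant or not. It also provides that the ECG is taken in triplicate at screening only. SAP Section 7.10 flags QTcF, PR and QRS in separate bullets: QTcF at three absolute thresholds (450, 480 and 500 msec), and PR and QRS by an absolute value combined with a change from baseline of at least 25%.

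**The concern.** A numeric ECG exclusion normally means that any one interval beyond its limit keeps the participant out. As written, the QTcF limit takes effect only when QRS or PR is already prolonged, and the QRS and PR limits take effect only when QTcF is long. Someone with a single abnormality is then handled by clinical judgment and not by the stated limit.

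Two sites could therefore reach opposite decisions on the same ECG. That matters because Section 6.6.1 forbids waivers and Section 11.2 treats entry of an ineligible participant as an important deviation: the same participant could be properly enrolled at one centre and a reportable deviation at another. The exposure that follows is 5 mg of ZYPREXA im and then a single 425 mg depot that releases drug over about a month (Section 2.1.3). There is no later depot dose to withhold, so screening is where a numeric limit does most of its work.

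**Working it through.** No power or sample-size figure is involved. The check is of the logic of the criterion and of whether another rule closes the gap.

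**1. The two readings.** Let Q be QRS ≥110 msec, P be PR ≥200 msec, and T be mean triplicate QTcF >450 msec (men) or >470 msec (women).

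- Literal reading of the numeric part: (Q or P) and T.
- List reading: Q or P or T.

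| Abnormalities present | Literal | List |
|---|---|---|
| none | no | no |
| T only | **no** | **yes** |
| Q only | **no** | **yes** |
| P only | **no** | **yes** |
| Q and P | **no** | **yes** |
| Q and T | yes | yes |
| P and T | yes | yes |
| Q, P and T | yes | yes |

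The literal reading excludes 3 of 8 combinations and the list reading 7 of 8; the four in bold change. These are logical cases, not equally likely ones, so 4 of 8 is not a share of participants.

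**2. Worked cases.** The last column shows which SAP Section 7.10 absolute QTcF thresholds the same value would exceed if seen after baseline.

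| Sex | QRS | PR | QTcF | Literal | List | SAP thresholds exceeded |
|---|---|---|---|---|---|---|
| M | 95 | 160 | 460 | no | yes | 450 |
| M | 95 | 160 | 481 | no | yes | 450, 480 |
| F | 95 | 160 | 481 | no | yes | 450, 480 |
| M | 112 | 160 | 420 | no | yes | none |
| M | 95 | 205 | 420 | no | yes | none |

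**3. Does any other rule set a numeric ECG limit that withholds dosing?**

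- Criteria a, n, cc and dd in Section 5.4 rest on history, clinical significance or Investigator discretion. None gives a QTcF, QRS or PR value.
- The recheck before ZYPREXA im (Section 5.5) covers inclusion criteria g and h and exclusion criterion a. Criterion m is not on it.
- The discontinuation criteria (Section 7.1) give numeric limits for hepatic enzymes and the leakage score only.
- The stopping rules (Section 7.4) grade laboratory results, not ECGs.
- ECG adverse events (Section 8.3.3) require worsening against baseline, so a QTcF already long at baseline is poorly caught.
- The SAP flags are summaries and do not act on dosing.

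Tables 1 to 4 schedule ECGs at seven visits up to and including R1 pre-dose: screening, days 3, 4, 5, 7 and 12, and R1. Only screening carries a numeric limit that acts on dosing, and that limit is criterion m. This count shows why the wording of m matters. It would be the same after the correction, so it does not measure the defect.

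**The case against.** The strongest reply is that the list reading is the natural one. The closing reference to other significant findings treats what precedes it as examples of significant findings. Within the same sentence, the *and* between the male and female limits cannot be a conjunction. The verb *have* seems to start a new statement about the participant and not to continue the description of the ECG. The protocol uses *and* loosely elsewhere: criterion w has "strong and moderate inducers or inhibitors of CYP1A2" where Section 6.8.1 has "strong or moderate inducers or inhibitors of CYP1A2". The strict reading also gives an odd result, since any degree of QRS or PR prolongation would pass if QTcF were normal. All of this stands as evidence of intent. It does not remove the literal reading: the sentence uses *or* for alternatives twice, so a careful site may take *and* to mean something different.

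A second reply is that the participant is still protected. A physician classifies every out-of-range ECG, a further ECG is scheduled on day 3 before the first dose, criterion a is rechecked, and the Investigator may discontinue anyone. This also stands, and a QTcF of 481 msec would come before a physician under either reading. But each safeguard rests on judgment, and none makes the stated limit binding.

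Third, the documents show little about the harm. The risk summary in Section 2.2.1 does not name QT prolongation, and nothing shows that sites have read m differently. Both points are fair and limit how much weight the concern can carry.

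**Conclusion.** The concern holds. On its literal wording the numeric part of criterion m misses an isolated long QTcF, an isolated long QRS, an isolated long PR, and long QRS with long PR when QTcF is normal. In those four of eight combinations exclusion depends on judgment, and no other rule supplies a numeric ECG limit that withholds dosing.

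This is most likely a drafting slip and not a deliberate choice, and the conclusion does not depend on which it is: an eligibility rule that can be applied two ways should be corrected. The number of participants affected cannot be derived from the documents. The point bears on participant safety and consistent eligibility across the roughly five centres. The primary PK summaries and the planned number of participants are unaffected.

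**What to change.** In Protocol Section 5.4, criterion m, replace *and have* with *or*, or set the limits out as separate bullets, any one of which excludes:

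- QRS ≥110 msec;
- PR ≥200 msec;
- mean of triplicate QTcF >450 msec (men) or >470 msec (women) at screening;
- any other ECG finding the Investigator judges clinically significant for participation.

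The sex-specific limits and the judgment part stay as they are, and the SAP needs no change.

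The cost is a small wording change. The triplicate screening ECG is already taken, so no test is added. Wording corrections to criteria r, s and bb were issued in Administrative Letter 01 and carried into Amendment 01, so there is precedent for a correction of this kind. The downside is possibly a few more screen failures, including for isolated QRS or PR prolongation; the documents do not allow an estimate. If the sponsor does intend isolated QRS or PR prolongation to be acceptable, the criterion should say so explicitly and still let the QTcF limit exclude on its own.

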5.5. Ongoing Confirmation of Participant Eligibility

Participants' continued eligibility will be reconfirmed by review of abbreviated inclusion and exclusion criteria prior to administration of ZYPREXA im. The abbreviated list will include the following inclusion criteria (g, h) and exclusion criterion (a). Clinical scales and laboratory tests taken on day 1 will be used to confirm eligibility on day 3. In case of a delay, laboratory results can be reviewed to perform abbreviated eligibility assessment on day 4, as long as this is done prior to administration of ZYPREXA im. Laboratory results from blood samples collected on day 4 are not required prior to initiating ZYPREXA im. Day 4 central clinical laboratory

assessments will serve as baseline values and are based on samples collected prior to dosing of ZYPREXA im. Serology to support eligibility criteria will only be done at screening.

5.6. Lifestyle Considerations

Participants will be required to comply with the following restrictions.

5.6.1. Meals and Dietary Restrictions

Participants are not required to fast before ZYPREXA im or any of the sc olanzapine extended-release injectable formulations.

Clinical laboratory tests (chemistry, hematology, coagulation, and urinalysis) will be performed following an overnight fast of at least eight hours at the time points detailed in [Table 1](#) to [Table 5](#). Non-fasting blood collection is permitted as needed, per the Investigator's assessment of AEs.

5.6.2. Caffeine, Alcohol, Tobacco, and Other Habits

It is recommended that participants do not consume alcohol and cannabis-derived products (such as marijuana) during the treatment period (excluding follow-up). Any positive result will be managed according to the Investigator's review and judgment, in consultation with the Sponsor's medical representative.

Excessive consumption of coffee, tea, and/or caffeine-containing beverages or food (ie, 600 mg or more of caffeine per day or five or more cups of coffee per day) will be prohibited for a minimum of 2 weeks before the first dose of trial drug and during the treatment period (excluding follow-up).

Participants must agree to maintain current smoking or nonsmoking status at the time informed consent is obtained and during the treatment period (excluding follow-up).

The use of tobacco products will be recorded at the visits indicated in [Table 1](#) to [Table 5](#). Use of cigars and pipes will be converted into cigarette use with a ratio of 1 cigar or pipe = 2.5 cigarettes. Use of vapes, e-cigarettes, nicotine gums, heat-non-burn tobacco products, snuffs, and nicotine patches will also be recorded but not be converted into cigarette use as these have minimal effect on CYP1A2 induction.

5.6.3. Physical Activity

Participants must remain lying down or semi-recumbent for safety reasons during administration of any of the 3 Olanzapine for Extended-release Injectable Suspensions (Fast-D, to-be-marketed, or Slow-C), and will remain under clinical observation for at least 3 hours after injection to monitor any possible symptom of PDSS.

Following the administration of ZYPREXA im or olanzapine extended-release sc injectable formulations, the participants should be advised to stand up from the lying position after waiting for 30 to 60 seconds in a sitting position at the bed margin, in order to reduce the risk of occurrence of orthostatic hypotension often associated with olanzapine treatment.

Participants will be instructed to not touch, rub, massage, or compress the injection site during the first 2 hours after administration of ZYPREXA im or olanzapine extended-release sc

injectable formulations. Participants may cover the injection site with loose-fitting clothing immediately after trial drug administration. Participants will not be allowed to lie on the injection site for the first 6 hours after the injection. Adhesive bandages may not be used during the period of leakage assessment following administration of olanzapine extended-release sc formulations.

During all treatment periods (excluding follow-up), participants are not to engage in strenuous exercise, and the use of hot tubs, steam baths, and saunas are prohibited.

